7.6.2 Adverse Events

An unsolicited AE is any AE reported by the participant that is either (1) not specified as a solicited AE in the protocol or (2) specified as a solicited AR in the protocol, but its onset occurs outside of the protocol-defined post vaccination period for reporting solicited AEs (ie, for the 7 days after each vaccination). A solicited ARs that meet the criteria for an SAE will also be recorded as an unsolicited AE.

A treatment-emergent AE (TEAE) is defined as any AE not present before exposure to vaccine or any AE already present that worsens in intensity or frequency after exposure. Only TEAEs are collected in this study.

An MAAE is defined as an AE that leads to an unscheduled visit to a healthcare practitioner.

Unsolicited AEs will be coded by PT and SOC using MedDRA and summarized by treatment, vaccination (first or second) and overall. Summaries for each vaccination will include AEs that occur during the 28 -day follow-up period after each vaccine.

All summaries of unsolicited AEs will present number and percentage of subjects in each category. For those summaries presented by PT, the preferred terms will be sorted in descending order of frequency within the mRNA-1893 treatment group.

7.6.2.1 Overview of Adverse Events

An overall summary of unsolicited TEAEs including the number and percentage of participants who experience the following will be presented:

- All unsolicited TEAEs
- All unsolicited serious TEAEs
- All unsolicited TEAEs leading to death

- All unsolicited TEAEs leading to vaccination discontinuation
- All unsolicited TEAEs of grade 3 or 4
- All unsolicited TEAEs of special interest
- All unsolicited medically-attended TEAEs

The table will also include number and percentage of participants with unsolicited, treatment-related TEAEs in each of the above categories.

The overall summary will also be summarized separately for flavivirus seropositive and seronegative participants.

In addition, listings containing individual participant data for TEAEs, TEAEs leading to vaccination discontinuation, SAEs, AESIs, and medically-attended TEAEs will be provided separately.

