3.5.2 Completion of Diary Card

At each vaccination visit (Day 1 and Day 29), study staff will provide a diary card to participants and training on its proper use. The participant will use the diary card for recording AE information; this information will be subject to potential change based on further questioning and/or follow-up by study staff.

Each participant will be instructed to complete the diary card to including the following:

- Solicited local and systemic reactogenicity AEs, as defined in Section 3.5.6, that
 occur on the day of each vaccine administration and during the 7 days after vaccine
 administration, with appropriate documentation to allow severity scoring by the
 investigator.
- Daily oral body temperature measurement should be performed at approximately the same time each day using the thermometer provided by the study site. If body

temperature is taken more than once in a given day, only the highest temperature reading should be recorded.

- Measurement, as applicable, for solicited local AEs; the size measurements will be performed using the ruler provided by the study site.
- All medications (excluding vitamins and minerals) taken on the day of each vaccine administration and during the 28 days after vaccine administration.
- Any unsolicited AE (Section 3.5.7) during the 28 days after each vaccine administration

During clinic visits, study staff will review the diary card information regarding solicited and unsolicited AEs, body temperature, and concomitant medications. This information will be recorded in the participant's source documents and the eCRF.

Diary cards will be the only source documents allowed for solicited systemic and local AEs (including body temperature measurements). The following additional rules apply to documentation of safety information collected using Diary Cards:

- No corrections or additions to the Diary Card will be allowed after it is delivered to the site.
- Any blank or illegible fields on the Diary Card must be described as missing data.
- The site staff must enter all readable entries in the Diary Cards into the eCRF.
- Any new safety information reported during the site visit (including a solicited reaction) must not be written into the Diary Card and must be described in the source documents as verbally reported event. Any adverse reaction reported in this manner must be described as an unsolicited reaction and therefore entered on the adverse event eCRF.

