Unsolicited AEs will also be evaluated by the investigator for the coexistence of any of the other following conditions:

• Medically attended AE, defined as an AE that leads to an unscheduled visit to a healthcare practitioner

Any solicited AE (Section 3.5.6) that meets any of the following criteria must be entered as an AE in the eCRF:

- Solicited local or systemic AE leading to the participant withdrawing from the study or the participant being withdrawn from the study by the investigator
- Solicited local or systemic AE lasting beyond 7 days post-vaccination
- Solicited local or systemic AE that leads to participant withdrawal from vaccine
- Solicited local or systemic AE that otherwise meets the definition of an SAE
- Laboratory test result or vital sign measurements with a toxicity score of Grade 3 or greater

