3.6.6.2 Safety Analyses

Reactogenicity will be summarized by dosing group (10, 30, 100, or 250 µg mRNA-1893 or placebo), vaccination (first or second dose), duration, and severity. Adverse events will be coded by preferred term and system organ class using MedDRA and summarized by dose group, vaccination (first or second dose), and overall. Adverse events will also be summarized by severity and relationship to the study vaccine. Descriptive statistics will be presented, and the difference in the proportion of participants with AEs will be provided, comparing each dose level with placebo pooled across all cohorts. Individual participant listings will be provided for all AEs, AEs leading to study withdrawal, AESI, MAAEs, and SAEs.

Safety data from clinical laboratory test results and vital sign measurements will be graded by severity scoring and analyzed by dose group and vaccination (first or second). Absolute and change from baseline values will be provided according to the toxicity table, along with mean, median, and standard deviation. Results of serology, urine drug screening, physical examinations, and pregnancy tests will be listed for all participants randomly assigned to receive study vaccine.

Medical history data for all participants randomly assigned to receive study vaccine will be presented by participant in a listing.

Baseline demographic and background variables will be summarized by dosing group for all randomly assigned participants. The number of participants who enroll in the study and the

number and percentage of participants who complete the study will be presented. Frequency and percentage of participants who withdraw or discontinue from the study and the reason for withdrawal or discontinuation will also be summarized.

Prior and concomitant medications will be listed (with start and stop dates) for each participant and summarized by common medical dictionary coding. Any vaccinations that occur during the trial will also be captured and summarized.

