7.6.1 Solicited Adverse Reactions

The term "reactogenicity" refers to selected signs and symptoms (ARs) occurring after vaccine administration that the participants are systematically asked to record. Participants will record such occurrences in a diary card on the day of each vaccine administration and for the 6 days after vaccine administration.

Date Issued: 25May2021

The local solicited ARs include injection site pain, injection site erythema, and injection site induration/swelling.

The systemic solicited ARs include fever, generalized myalgia (muscle ache or pain), generalized arthralgia (joint ache or pain), headache, fatigue/malaise (unusual tiredness), nausea/vomiting, chills, and rash.

For erythema, swelling, and fever, grade will be derived based on the measurement recorded on the diary card as noted in Table 2. Other events will be assessed for grade by the investigator based on the Toxicity Grading Scale for Healthy Adult and Adolescent Volunteers Enrolled in Preventative Vaccine Clinical Trials [DHHS 2007] and recorded in the eCRF.

Table 2: Toxicity Grads for Erythema, Swelling, and Fever

| | Grade 1 | Grade 2 | Grade 3 | Grade 4 |
|----------|---------------|---------------|---------------|----------|
| Erythema | 21 - 50 mm | 51 – 100 mm | > 100 mm | |
| Swelling | 21 – 50 mm | 51 – 100 mm | > 100 mm | |
| Fever | 38.0 – 38.4°C | 38.5 – 38.9°C | 39.0 – 40.0°C | > 40.0°C |

Any solicited AR that meets any of the following criteria will be entered as an AE in the eCRF:

- Solicited local or systemic AR leading to the participant withdrawing from the study or the participant being withdrawn from the study by the investigator
- Solicited local or systemic AR lasting beyond 7 days post vaccination
- Solicited local or systemic AR that leads to participant withdrawal from vaccine
- Solicited local or systemic AR that otherwise meets the definition of an SAE
- Laboratory test result or vital sign measurements with a toxicity score of Grade 3 or greater or that is deemed clinically significant by the investigator for any grade

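### The SAP's summary row for vaccination discontinuation omits non-serious, in-window, diary-recorded solicited reactions that stop vaccination

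*SAP*

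**What the plan says.** SAP 7.6.2.1 plans an overview of unsolicited TEAEs. One row is "All unsolicited TEAEs leading to vaccination discontinuation", and every row is repeated for treatment-related events. The same section plans "listings containing individual participant data for TEAEs, TEAEs leading to vaccination discontinuation, SAEs, AESIs, and medically-attended TEAEs will be provided separately"; that listing is not restricted to unsolicited events.

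SAP 7.6.2 calls an event unsolicited if it is not a solicited term, or if it is "specified as a solicited AR in the protocol, but its onset occurs outside of the protocol-defined post vaccination period for reporting solicited AEs". It then adds one exception: "A solicited ARs that meet the criteria for an SAE will also be recorded as an unsolicited AE".

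SAP 7.6.1 lists the solicited reactions that must also be entered as AEs in the eCRF. One item is "Solicited local or systemic AR that leads to participant withdrawal from vaccine". Protocol 3.5.7.1.1 has the same item: "Solicited local or systemic AE that leads to participant withdrawal from vaccine".

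Protocol 3.5.2 deals with a reaction first mentioned verbally at a visit: "Any adverse reaction reported in this manner must be described as an unsolicited reaction and therefore entered on the adverse event eCRF".

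On study withdrawal, protocol 3.6.6.2 says: "Individual participant listings will be provided for all AEs, AEs leading to study withdrawal, AESI, MAAEs, and SAEs". SAP 7.6 names AEs leading to study withdrawal among the safety assessments. SAP 7.6.2.1 to 7.6.2.3 give them no listing of their own. SAP Section 8 records two other departures from the protocol but not this one.

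**The concern.** SAP 7.6.1 sends several kinds of solicited reaction to the AE page, but SAP 7.6.2 reclassifies only the serious ones as unsolicited. A reaction that stops vaccination without being serious is therefore an AE record that the discontinuation row excludes.

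Safety, tolerability and reactogenicity across dose levels are the primary objective. A reader comparing doses would naturally go to the row on AEs that ended vaccination and might take it as complete. The row can also disagree with the listing in its own section. Whether a given reaction is counted can depend on whether the participant wrote it in the diary or mentioned it at a visit, which has nothing to do with dose.

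**Working it through.** **The plan's own figure.** Protocol 3.6.4 and SAP 5.2 give the chance of seeing at least one AE among 24 vaccinees per dose level as 1 − (1 − p)^24.
- p = 0.10: 1 − 0.90^24 = 0.920 (stated 92%).
- p = 0.05: 1 − 0.95^24 = 0.708 (stated 70.8%).

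Both reproduce, and no stated number is in dispute. The denominator of 24 is used below.

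**Tracing one case through the definitions.** Take a non-serious solicited systemic reaction with onset on Day 2, recorded in the diary, after which the participant receives no second dose because of it.
1. AE page: required by SAP 7.6.1 and protocol 3.5.7.1.1.
2. Unsolicited under SAP 7.6.2? It is a solicited term, its onset is inside the window, and it is not an SAE. So no.
3. Discontinuation row in SAP 7.6.2.1 and its related version: limited to unsolicited TEAEs, so not counted.
4. Tables in SAP 7.6.2.2 and 7.6.2.3: all limited to unsolicited TEAEs, so not counted.
5. Solicited tables in SAP 7.6.1: counted by grade, with duration summarised, but nothing shows that vaccination stopped.
6. Listing of TEAEs leading to vaccination discontinuation in SAP 7.6.2.1: included, because a TEAE is any AE not present before exposure.
7. Disposition table in SAP 7.2: counted under the reason for stopping vaccination, by treatment group and serostatus. The SAP does not say that the event or its relatedness is shown.

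**Solicited reactions that do reach the row.** There are three routes: the reaction is serious (SAP 7.6.2), its onset is after the window (SAP 7.6.2), or it is first reported verbally at a visit (protocol 3.5.2).

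**Scale.** Each omitted participant lowers a dose-group rate by 1/24 = 4.2 percentage points. SAP 7.1 names the Clopper-Pearson method for percentages. With n = 24:
- 0/24: upper limit 1 − 0.025^(1/24) = 14.2%, so 0 to 14.2%.
- 1/24 = 4.2%: lower limit is the 2.5% point of Beta(1, 24) = 0.1%; upper limit is the 97.5% point of Beta(2, 23) = 21.1%.
- 2/24 = 8.3%: lower limit is the 2.5% point of Beta(2, 23) = 1.0%; upper limit is the 97.5% point of Beta(3, 22) = 27.0%.

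The counts of 1 and 2 are assumptions chosen to show scale. The documents give no expected number.

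**The case against.** The strongest reply is that nobody is lost. The listing in SAP 7.6.2.1 is unrestricted, and the disposition table compares doses on reasons for stopping vaccination without using the unsolicited flag. The row sits in a table headed as unsolicited and is correctly labelled, so 0/24 would be right for what it claims to count. The SAP also never states that AE-page solicited reactions are to be excluded; a programmer might treat every AE-page record as unsolicited.

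Much of this stands. It reduces the defect to an incomplete summary row. It does not remove it, because the listing gives no rates and the disposition table need not name the event or its relatedness. The programmer's reading would contradict the definition in SAP 7.6.2 and would place in-window solicited reactions in the unsolicited tables as well as the solicited ones.

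Two stronger readings are tempting, and the documents support neither.
- A reader might infer that everyone who stops because of a solicited reaction is left out of the row. Serious, late-onset and verbally reported reactions can all enter it.
- A reader might infer that AEs leading to study withdrawal go unreported, or that the protocol promised a table row for them. Protocol 3.6.6.2 promises a listing of these AEs and, separately, withdrawals by reason. SAP 7.2 delivers the second, with a disposition listing, and protocol 3.3.1 includes SAE and non-serious AE among the reasons. The events also fall within the all-TEAE listing. Only the dedicated listing is missing.

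It is also fair to say that the documents nowhere describe solicited reactions as a likely reason for missing the second dose.

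**Conclusion.** Under the SAP's own definitions, the vaccination-discontinuation row and its treatment-related version leave out non-serious, in-window, diary-recorded solicited reactions that end vaccination. No other AE summary table counts them as discontinuations. The participants remain visible in the unrestricted listing and in disposition, so the fault is incomplete summarisation of a tolerability output, not loss of data.

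The size is 4.2 percentage points per omitted participant in a dose group of 24. How many there would be is unknown, and if there are none the row is unaffected. The conclusion rests on reading SAP 7.6.2 as written; if another reading was intended, the SAP has to state it.

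The missing listing of AEs leading to study withdrawal is a minor, separate gap. It would not justify a change on its own.

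**What to change.** In SAP 7.6.2.1, add or substitute a row for any AE or solicited AR leading to discontinuation of vaccination, with solicited and unsolicited sub-rows and a treatment-related version. Identify events by the recorded discontinuation reason or action, not by the unsolicited flag. State that in-window solicited reactions entered on the AE page only because they ended vaccination stay out of the other unsolicited tables.

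Secondly, add the listing of AEs leading to study withdrawal planned in protocol 3.6.6.2, or record its omission in SAP Section 8.

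The cost is SAP wording, a little programming, one more table row with its sub-rows, and one listing. The reactions are already required on the AE eCRF, and protocol 3.3.2 requires reasons for withdrawing vaccination to be recorded. The eCRF itself is not among the documents, so the field linking an event to discontinuation should be confirmed; the existing row already presupposes one.

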7.6.2.2 TEAEs by Preferred Term

The following summary tables of TEAEs will be provided by MedDRA PT using frequency counts and percentages (i.e., number and percentage of participants with an event). When summarizing the number and percentage of participants with an event, participants with multiple occurrences of the same AE or a continuing AE will be counted once. Only the maximum severity level will be presented and an AE with missing severity will be counted as Grade 3/severe in the severity summaries. Only the strongest relationship level will be presented and an AE with missing relationship will be counted as related in the relationship summaries.

- All unsolicited TEAEs
- All unsolicited TEAEs by relationship to the study vaccine
- All unsolicited TEAEs by toxicity grade
- All unsolicited TEAEs occurring within 28 days of any vaccination by vaccination
- All unsolicited TEAEs within 28 days of any vaccination by vaccination and toxicity grade

7.6.2.3 TEAEs by System Organ Class and Preferred Term

The following summary tables of TEAEs will be provided by MedDRA SOC and PT using frequency counts and percentages (i.e., number and percentage of participants with an event) for all participants, for all flavivirus seropositive participants and for all flavivirus seronegative participants. When summarizing the number and percentage of participants with an event, participants with multiple occurrences of the same AE or a continuing AE will be counted once. Only the maximum severity level will be presented and an AE with missing severity will be counted as Grade 3/severe in the severity summaries. Only the strongest relationship level will be presented and an AE with missing relationship will be counted as related in the relationship summaries.

- All unsolicited TEAEs
- All unsolicited treatment-related TEAEs
- All unsolicited TEAEs through 7 days after any vaccination
- All unsolicited treatment-related TEAEs through 7 days after any vaccination
- All unsolicited TEAEs of Grade 3 or higher through 7 days after any vaccination
- All unsolicited treatment-related TEAEs of Grade 3 or higher through 7 days after any vaccination
- All unsolicited TEAEs of Grade 2 or higher through 7 days after any vaccination
- All unsolicited treatment-related TEAEs of Grade 2 or higher through 7 days after any vaccination
- All unsolicited TEAEs of Grade 3 or higher through 28 days after any vaccination
- All unsolicited treatment-related TEAEs of Grade 3 or higher through 28 days after any vaccination
- All unsolicited TEAEs of Grade 2 or higher through 28 days after any vaccination
- All unsolicited treatment-related TEAEs of Grade 2 or higher through 28 days after any vaccination

- All unsolicited TEAEs within 60 minutes after any vaccination
- All unsolicited treatment-related TEAEs within 60 minutes after any vaccination
- All unsolicited serious TEAEs after any vaccination
- All unsolicited serious treatment-related TEAEs after any vaccination
- All unsolicited TEAEs of special interest after any vaccination
- All unsolicited treatment-related TEAEs of special interest after any vaccination

7.6.3 **Clinical Laboratory Evaluations**

All laboratory test results will be presented in the data listings. The results that are outside the reference ranges will be flagged in the data listings. The abnormalities meeting the toxicity grading criteria (Grade 2 or higher) in any safety laboratory will be listed separately. If a participant has a laboratory test with Grade 2 or higher abnormality at any post vaccination visit, then all results for that participant and laboratory test will be presented in the listing.

For continuous hematology, serum chemistry, and coagulation measurements, the observed values and changes from Baseline will be summarized at each scheduled visit by treatment groups as defined in Section 7.1. Shift from baseline in the toxicity grades to the worst post-vaccination result will be summarized by treatment group and vaccination (first or second). All scheduled and unscheduled assessments will be considered when determining the worst post-vaccination result.

Incidence of laboratory abnormalities of Grade 2 or higher after any vaccination and through 7 days after any vaccination will be summarized by treatment group.

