6	Any ≥ Grade 3 unsolicited adverse event in an mRNA-1893 cohort ^b that cannot be reasonably attributed to a cause other than vaccination OR Any ≥ Grade 3 laboratory abnormality ^c in an mRNA-1893 cohort ^b that cannot reasonably be attributed to a cause other than vaccination	≥ 20% and ≥ 2 participants/group	

^a For the first 5 participants in each dose level cohort, the pause rule will be considered met if 2 of the first 5 participants experience the same event regardless of dosing group.

If a pause is triggered in the study, each participant's clinic visits will continue until the next scheduled vaccination visit. If a pause affects a participant's vaccination visit, the window for that participant's vaccination visit will be suspended until the pause is lifted and vaccination can resume. Once the pause is lifted at a site, vaccination should be reinstated as soon as possible. Clinic visits should thereafter (Day 36 [+3 days], Day 57 [-7/+14 days], Month 7 [± 14 days], and Month 13 [± 14 days]) be scheduled as if participants had received their second vaccination within the 28 (+14) day window. The Dose 2 window may be extended to 28 (+14) days at the discretion of the principal investigator and with approval of the study medical monitor on a case by case basis for participants whose window is affected by a study pause.

b The rate of adverse events and laboratory abnormalities will be computed based on the number of exposed participants who have provided safety data (i.e., have completed a post-dosing visit for assessment of safety).

Grading of laboratory parameters will be based on the US Food and Drug Administration Guidance for Industry "Toxicity grading scale for healthy adult and adolescent volunteers enrolled in preventive vaccine clinical trials" (DHHS 2007).

If a pause is prolonged such that the second vaccination takes place outside the 28 (+14) day window, the Sponsor has the option to add additional participants in a dosing cohort to achieve the original number of participants planned for dosing within the 28 (+14) day window. If a participant is in the Screening Phase for more than 28 days as the result of a pause, the participant may be rescreened for study eligibility (and will receive a new screening number) as long as the participant continues to provide consent to participate in the study.

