7.1 General Considerations

Participants will be identified in the listings by the participant identification number concatenated with the site number. For rescreened participants, only the data collected from the last screening will be presented in the data listings and included in the summaries.

Data from participants excluded from an analysis set will be presented in the data listings but not included in the calculation of summary statistics for the corresponding analysis set.

Although date of physical exam is collected in the eCRF, this data will not be presented in the data listings.

The following treatment groups will be used for summary purposes:

- Placebo
- mRNA-1893 10 μg
- mRNA-1893 30 μg
- mRNA-1893 100 μg
- mRNA-1893 250 μg
- mRNA-1893 Total

For categorical variables, frequencies and percentages will be presented. Continuous variables will be summarized using descriptive statistics (number of participants, mean, median, standard deviation [SD], minimum, and maximum). See Appendix B for variable display standards.

When count data are presented, the percentage will be suppressed when the count is zero in order to draw attention to the non-zero counts. A row denoted "Missing" will be included in count tabulations where specified on the shells to account for dropouts and missing values. The denominator for all percentages will be the number of participants in that treatment within the analysis set of interest, unless otherwise specified.

For the change from Baseline safety summaries, Baseline will be defined as the last non-missing measurement (including repeated and unscheduled assessments) before the first vaccination.

For the immunogenicity analyses, Baseline will be defined as the last non-missing assessment collected at Visit Day 1.

Study Day relative to the first vaccination will be calculated as below:

- Study Day prior to the first vaccination will be calculated as: date of assessment/event date of the first vaccination;
- Study Day on or after the date of the first vaccination will be calculated as: date of assessment/event date of the first vaccination + 1;

Study Day relative to the most recent vaccination will be calculated as below:

- Study Day prior to the first vaccination will be calculated as: date of assessment/event date of the first vaccination;

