- Study Day on or after the date of the first vaccination but before the second vaccination (if applicable) will be calculated as: date of assessment/event date of the first vaccination + 1;
- Study Day after the date of the second vaccination will be calculated as: date of assessment/event date of the second vaccination + 1; if Study Day is on the same day as the second vaccination, date and time will be compared with the second vaccination date and time. If it is prior to the second vaccination, then study Day is calculated as: date of assessment/event date of the first vaccination + 1; If it is after the second vaccination then Study Day is calculated as: date of assessment/event date of the second vaccination + 1.

For GMT calculation, antibody values reported as below LLOQ will be replaced by $0.5 \times LLOQ$. Values that are greater than the upper limit of quantification (ULOQ) will be converted to the ULOQ. Missing results will not be imputed.

Date Issued: 25May2021

The following timeframes will be defined for reporting safety data in this study:

- Vaccination: First vaccination on Day 1 to 28 days after last vaccination. If a participant receives two vaccinations, this stage starts at the first vaccination on Day 1 and continues through the 28th Day after the 2nd vaccination.
- Within 28 days of vaccination: Consists of all periods that begin with a vaccination and continue through the 28th Day after the vaccination. This is a subset of the vaccination stage. If a participant receives two vaccinations, this stage includes the two 28-Day periods that begin after each vaccination.
- Overall: Begins at the first vaccination on Day 1 and continues through the final safety call.

Analysis sets for the various analyses are defined in Section 6.

The 95% confidence interval (CI) for percentage will be obtained from SAS procedure of Proc Freq using Clopper-Pearson method. The 95% CI for GMT will be calculated based on the t-distribution of the log-transformed values then back transformed to the original scale for presentation.

Expected visit windows for all study assessments are detailed in Appendix A.

All analyses will be conducted using SAS Version 9.4 or higher.

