10.1 Appendix A Analysis Visit Windows for Safety and Immunogenicity Analysis

Table 3 Visit Window Mapping Rules

| Table 3 Visit Window Mapping Rules | | |
|---------------------------------------|--|----------------------------|
| Labs (Hem | atology, Chemistry, and Coagulation) and | l Vital Signs |
| Visit | Target Study Day | Visit Window |
| Day 1 | Date of First Vaccination (1) | Pre-dose |
| Day 1, 1 hour postdose – Vitals only | 1 | ≥ 1 hour post-dose |
| Day 8 - Labs only | 8 | [8,11] |
| Day 29 | Date of Second Vaccination (29) | [29,36] |
| Day 29, 1 hour postdose – Vitals only | 29 | ≥ 1 hour post-dose |
| Day 36 - Labs only | 36 | [36,39] |
| Day 57 (Month 2) – Labs only | 57 | [50,64] |
| | Adverse Events | |
| Stage | Vaccination | Target Time Frame |
| Vaccination | All | [1, 57] |
| Short-Term Follow-up | First | [1,29] |
| | Second | [29,57] |
| Long-Term Follow-up | First | NA |
| | Second | [57, Month 12 Safety Call] |
| Overall | All | [1, Month 12 Safety Call] |

Protocol mRNA-1893-P101

| Immunogenicity | | | | | |
|-------------------------------------|-------------------------------|------------|--|--|--|
| Visit Target Study Day Visit Window | | | | | |
| Day 1 | Date of First Vaccination (1) | Pre-dose | | | |
| Day 29 | 29 | [29,36] | | | |
| Day 57 (Month 2) | 57 | [50,64] | | | |
| Month 7 | 196 | [182,210] | | | |
| Month 13 | 364 | [343, 385] | | | |

Protocol mRNA-1893-P101

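### The 7-day limit on the early laboratory abnormality table (SAP 7.6.3), read as a date, admits only the first of the four permitted Day 8 and Day 36 draw days, so the early rate can be understated

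*SAP*

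**What the plan says.** The sentence at issue is in SAP 7.6.3 (Clinical Laboratory Evaluations): "Incidence of laboratory abnormalities of Grade 2 or higher after any vaccination and through 7 days after any vaccination will be summarized by treatment group". It asks for two versions of one table, one without a time limit and one limited to 7 days, the latter in the words "through 7 days after any vaccination will be summarized by treatment group".

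The timing of the draws comes from three places:

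- SAP Appendix A, Table 3, sets the laboratory windows as "Day 8 - Labs only | 8 | [8,11" and "Day 36 - Labs only | 36 | [36,39", that is, Study Days 8 to 11 and 36 to 39. SAP 7.1 gives these windows general reach: "Expected visit windows for all study assessments are detailed in Appendix A".
- Protocol Table 5 allows +3 days and nothing early for both visits. Protocol 3.4.2.2 repeats this for the second: "Day 36 [+3 days], Day 57 [-7/+14 days".
- SAP 7.1 makes the day of the first vaccination Study Day 1, in the rule that begins "Study Day on or after the date of the first vaccination will be calculated as".

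On denominators, SAP 7.1 says: "The denominator for all percentages will be the number of participants in that treatment within the analysis set of interest, unless otherwise specified". For laboratory data the analysis set is the Safety Set (SAP 7.6).

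**The concern.** The Day 8 and Day 36 draws are the only scheduled samples meant to show an early laboratory effect. Their windows open on the last day that a 7-day limit permits and run for three more days. A site that follows the protocol exactly can therefore produce a draw that the table leaves out. Because the default denominator is the whole treatment group, the omission does more than lose precision. A participant with a Grade 2 result on Study Day 10 would be counted among those without one.

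Safety is the primary objective and each dose level has only 24 vaccinated participants, so a few misplaced results change what the table shows. The version without a time limit does not fill the gap, because it also takes in the Day 29 and Day 57 draws.

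**Working it through.** **Inputs.** Draw windows [8,11] and [36,39] (SAP Appendix A); vaccination day = Study Day 1 (SAP 7.1); full-group denominator (SAP 7.1); 24 vaccinated per dose level (Protocol 3.6.4, SAP 5.2). The share *f* of scheduled draws made on exactly the 7th day after the dose is not in the documents and is varied as an assumption.

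**Step 1: the plan's own figure.** The chance of at least one affected participant in 24 is 1 − (1 − p)^24. At p = 0.10 this is 0.9202 and at p = 0.05 it is 0.7080. These reproduce the stated 92% and 70.8%.

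**Step 2: days after the dose.** For dose 1, Study Day minus 1 turns 8 to 11 into 7, 8, 9 and 10 days. For a dose given on Day 29, subtracting 29 turns 36 to 39 into the same 7, 8, 9 and 10 days. One of the four permitted days meets a 7-day date limit.

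**Step 3: what the phrase means elsewhere in the SAP.**

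- SAP 6.1.3 equates the 7 days following a vaccination with Day 1 through Day 8, a date range ending on Day 8.
- SAP 7.6.2.3 applies the same limit to adverse events, which have no visit window.
- SAP 7.6.4 applies it to vital signs. These are not scheduled at Day 8 or Day 36 (Protocol Table 5; both rows of Appendix A are marked for laboratory data only), so there it cannot stand for those visits.
- SAP 7.6.3 refers to scheduled visits when it wants a by-visit summary, and does not do so in the incidence sentence.

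SAP 7.3 is tighter still for medications: its 7-day period is the vaccination day plus 6 days. On that convention even a Study Day 8 draw would be outside.

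**Step 4: size under a date cut-off.** For one dose, tabulated rate = p × f. This assumes no unscheduled draws and an abnormality that would be found on any day of the window.

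| Share on 7th day (assumed) | True 10% shows as | Chance of ≥1 in 24 | True 5% shows as | Chance of ≥1 in 24 |
|---|---|---|---|---|
| 0.25 | 2.5% | 45.5% | 1.25% | 26.1% |
| 0.50 | 5.0% | 70.8% | 2.5% | 45.5% |
| 0.75 | 7.5% | 84.6% | 3.75% | 60.0% |
| 0.90 | 9.0% | 89.6% | 4.5% | 66.9% |
| 1 (or visit window) | 10% | 92.0% | 5% | 70.8% |

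**Step 5: pooling over two doses.** The table covers any vaccination.

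- If abnormalities after the two doses are independent at 10% each, the true any-dose rate is 1 − 0.90² = 19.0%. At f = 0.25 the table shows 1 − 0.975² = 4.94%, and at f = 0.90 it shows 1 − 0.91² = 17.19%.
- If the same 10% of participants are abnormal after both doses and draw days are independent, the table shows 10% × [1 − (1 − f)²]. This is 4.4% at f = 0.25 and 9.9% at f = 0.90.

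The second case is milder. The direction is the same in both.

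**The case against.** The best reply is that the limit means the visit, not the calendar. Protocol 3.5.8 describes the Day 8 and Day 36 laboratory work as testing at 7 days after vaccination, and Appendix A maps the late-in-window draws to those visits. On that reading the window itself causes no loss. This has some weight, because the SAP never defines the limit for this table, but it does not fit the SAP's use of the phrase for adverse events and vital signs. The visit reading also has a gap of its own. Study Days 36 to 39 suit a second dose given on Day 29, but the protocol allows that dose up to 14 days later. After a dose on Day 40, the 7-day draw is on Day 47, outside the mapped window.

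Other parts of the reply stand:

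- A reader might infer that the table counts nothing but 7th-day blood. That goes too far: Protocol 3.5 allows unscheduled visits at any time, and the incidence sentence does not exclude their results.
- A reader might infer that three quarters of draws are lost. That needs draws spread evenly over the four days, and the documents give no such distribution. The target is Day 8.
- A reader might infer that differences in visit timing between sequential cohorts could pass for a dose effect. Nothing in the documents suggests that timing differs by cohort.
- The denominator rule is a default, and SAP 7.1 leaves the use of a row for missing values to the table shells, which are not available.
- The results are not lost. SAP 7.6.3 also provides by-visit values and changes, a shift to worst grade by vaccination that includes unscheduled results, and a listing of Grade 2 or higher abnormalities. Protocol 3.5.8 has Grade 3 or greater values entered as adverse events. Pause rule 6 has no 7-day limit and uses its own denominator.

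**Conclusion.** The point holds as a defect in how one safety table is specified. Applied as the SAP uses the phrase elsewhere, the 7-day limit excludes on-schedule draws made 8 to 10 days after the dose, and the default denominator then counts those participants as free of abnormality. The per-dose rate is multiplied by the share of draws on the 7th day. A true 10% shows as 2.5% to 9% for assumed shares of 0.25 to 0.90. The understatement is zero if all draws are on that day or if the visit window was intended.

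The documents do not show that an early signal would be missed, or that escalation or pausing depends on this table. What would be missing is a correct early incidence. The by-visit summaries give values and changes, the shift table takes the worst result over a longer period, and the unlimited version mixes in Day 29 and Day 57.

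**What to change.** In SAP 7.6.3, replace the 7-day limit in the laboratory incidence sentence with: *from each vaccination through 10 days after that vaccination (covering the Day 8 and Day 36 visits with their +3-day window, counted from the actual date of each dose), including unscheduled and repeat results*. State that the denominator is participants with at least one laboratory result in that period.

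Counting from the actual dose keeps the early draw in the table when the second dose is late. Starting at the dose, instead of at the visit window, keeps unscheduled results from the first 6 days.

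The cost is one SAP sentence, a relabelled table, and a period 3 days longer than that of the 7-day adverse event tables, which a footnote can state.
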